7.9 Exploratory Analyses

7.9.1 Analysis of Monitoring Biomarkers

Each intervention included in the PrecISE master protocol has specified one or more monitoring biomarkers hypothesized to provide evidence of early clinical response to that intervention. Exploratory analyses will be conducted at the end of the study to investigate the utility of these biomarkers as potential early or intermediate outcomes (efficacy or safety) for future clinical trials of the interventions. To this end, models like those described above for the primary efficacy analysis will be fit with a particular intervention's monitoring biomarker as outcome to determine if treatment effects are detected. We will evaluate the correlation between each monitoring biomarker and each of the two primary outcomes.

7.9.2 Analysis of Adolescents

The efficacy of the subset of interventions available for testing in adolescents (MCT and Broncho-Vaxom) will be analyzed using the same approach as for the overall population (i.e., the MMRM and log linear models described in Section 7.4) but with the analysis population restricted to adolescents. We anticipate these analyses to be descriptive in nature, due to the lack of power for the limited number of adolescents expected to be enrolled (~40).

Safety data will also be described and analyzed separately for the adolescent population using the same tables and graphics described for the overall population.

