Spiro PRE with specified med withholds 	X	X		X	X	X	X	X	X	X 
Spiro POST 4 puffs albuterol 				X	X				X	
Maximum Bronchodilator (4 + 2 + 2 puffs albuterol)	X			X 						
Methacholine challenge (if needed)		X								
DLCO (if needed bc +smoking Hx)		X								
Cotinine (if needed bc +smoking Hx)		X								
ACQ-6 	X			X	X	X	X	X	X	X
Exacerbation History/Health care utilization questionnaire 	X			X	X	X	X	X	X	X
Safety Assessments										
Urine: Pregnancy test (females of childbearing potential)	X	X		X	X	X 	X	X 	X	X 
Blood: CBC with Differential Count				X	X	X 	X	X 	X	X 
Blood: Chemistry Panel (including liver function tests)				X	X	X 	X	X 	X	X 
Blood: Triglycerides (non-fasting)				X						

PrecISE Visit Structure										
Procedures	Visit SA: Screening	Visit SB: Optional as needed to qualify	Visit SC: Compliance check*	Visit O: Run-In Visit, Safety Labs & Biomarkers	Visit X.1: Treatment Visit 1	Visit X.2: Treatment Visit 2	Visit X.3: Treatment Visit 3	Visit X.4: Treatment Visit 4	Visit X.5: End of Treatment Visit	Visit X.6: Washout
Blood: Viral screens – Hep B and C, HIV Types 1 and 2				X						
Blood: TB via QuantiFERON 				X						
Radiology (CXR), not required if the participant has a negative QuantiFERON 				X						
Cardiology (EKG)				X						
Adverse event assessment 	X	X	X	X	X	X	X	X	X	X
Primary Predictive Biomarkers										
Blood eosinophils (CBC with diff)				X	X					
Plasma IL-6				X						
FeNO				X	X					
Genotyping				X						
Response/pharmacodynamic biomarkers										
Blood eosinophils (CBC with diff)						X 	X	X 	X	X 
Plasma IL-6										
FeNO						X 	X		X	
Additional Phenotyping Procedures										
Sputum induction 				X						
CT scan for lung phenotyping 				X						
Blood: PBMCs 					X 				X	
Urine for biorepository					X		X		X	
Blood for RNA 				X						
Other blood (plasma, serum) for biorepository					X	X 	X	X 	X	
Nasal EPX 				X	X		X		X	

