\*Visit SC is optional. All other visits are approximately 4 weeks apart. Treatment visits X.1-X.6 are repeated each treatment period.

These procedures and assessments may be conducted remotely via phone, videoconference or electronic survey methods.

 Spirometry may be conducted in the home and/or in the clinic.

 Optional at site discretion to demonstrate reversibility

 Not required for adolescents at VX.2 and VX.4.

 Blood for TB via QuantiFERON is collected on adults only

 If not collected before V1.1, the Sputum and CT can be collected before or at V2.1 or before or at V3.1.

Sputum induction and CT scans may not be conducted at all sites.

 PBMCs may not be collected at all sites.

 PBMC is only collected at V1.1.

 Blood for RNA if not collected before V1.1, should be collected at V2.1, and, again, at V3.1.

 Nasal EPX can be skipped if the institution requires a COVID test before the procedure. Nasal EPX collection is optional at the site level.

 Not required at the final VX.6.

Note: Due to the COVID-19 pandemic, not all procedures will be conducted at all clinic visits.

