## 7 STUDY INTERVENTION DISCONTINUATION AND PARTICIPANT DISCONTINUATION/WITHDRAWAL

### 7.1 DISCONTINUATION OF STUDY INTERVENTION

#### 7.1.1 DISCONTINUATION OF A PARTICIPANT'S ASSIGNED INTERVENTION

Participants will be monitored for safety during the trial and the occurrence of certain adverse events or laboratory abnormalities will result in discontinuation from the participant's current treatment; that is, participation in the current treatment period will stop, and the participant will enter the washout period. The following adverse events or lab abnormalities will result in discontinuation from the participant's current treatment:

1. Serious infection (including pneumonia, cellulitis, kidney or neurologic infections, and any bacteremia/sepsis).
2. Any bleeding event thought to be associated with a platelet count reduction per the judgment of the center investigator.
3. Any other adverse event, per judgment of the center investigator, requiring discontinuation from treatment.
4. Laboratory values are monitored per the schedule of activities in Section 1.3. For adults, the below lab tests will be assessed at every 4-week visit during the treatment period. Abnormalities in the following laboratory values require prompt retesting within 3 to 5 days:
  - ANC <1000/ $\mu$ L for black participants, <1500/ $\mu$ L for other participants.
  - Lymphocyte count <500/mm^3.
  - Platelet count <50,000/mm^3.
  - Hemoglobin <9.0 g/dL.
  - AST and/or ALT elevation >3 times the upper limit of normal.
  - Bilirubin  $\geq$ 2 times the upper limit of normal.
  - Calculated eGFR < 54 mL/min/1.73 m^2 and baseline eGFR was >60 mL/min/1.73 m^2 OR calculated eGFR < 50 mL/min/1.73 m^2 and baseline eGFR was 54-60 mL/min/1.73 m^2

If both tests violate the following cut-off values, the participant is removed from treatment:

- a. Two sequential platelet counts <50,000/mm^3.
- b. One platelet count <25,000/mm^3 unless the confirmatory test demonstrates a count >50,000/mm^3. Treatment must be withheld pending the confirmatory retest.
- c. Two sequential neutrophil counts <500/mm^3.
- d. Two sequential lymphocyte counts <500/mm^3.
- e. Two sequential hemoglobin assessments <8.0 g/dL or >30% below the participant's initial baseline value or the baseline value for the current treatment period.

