#### 8.3.5.4 TIME PERIOD AND FREQUENCY FOR EVENT ASSESSMENT AND FOLLOW-UP

The occurrence of an adverse event (AE) or serious adverse event (SAE) may come to the attention of study personnel during study visits and interviews of a study participant presenting for medical care, or upon review by a study monitor.

All AEs including local and systemic reactions not meeting the criteria for SAEs will be captured on the appropriate case report form (CRF). Information to be collected includes event description, time of onset, clinician's assessment of severity, relationship to study intervention (assessed only by those with the training and authority to make a diagnosis), and time of resolution/stabilization of the event. All AEs must be documented appropriately regardless of relationship. All AEs will be followed to adequate resolution.

Any medical condition that is present at the time that the participant is screened will be considered as baseline and not reported as an AE. However, if the study participant's condition deteriorates at any time during the study, it will be recorded as an AE.

Changes in the severity of an AE will be documented to allow an assessment of the duration of the event at each level of severity to be performed. AEs characterized as intermittent require documentation of onset and duration of each episode.

A site physician investigator or sub-investigator will record all reportable events between the time the participant provides informed consent through 8 weeks after their last treatment or a period corresponding to five half-lives of the treatment last received, whichever is longer (Section 4.1). At each study visit, the investigator will inquire about the occurrence of AE/SAEs since the last visit. Events will be followed for outcome information until resolution or stabilization.

---

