1.4 Document Disposition

This document describes the planned statistical analyses that will be conducted at interim analysis points and at the completion of the study of each of the interventions. Once the initial unblinded data review has occurred for an intervention, only the blinded statistics team members will be allowed to modify the Statistical Analysis Plan.

2. Objectives, Endpoints, and Estimands

The PrecISE study has two primary objectives:

1. Identify novel therapies that work in biomarker-defined subgroups of severe asthma patients
2. Optimize the subgroups targeted for treatment by refining the biomarkers and subgroup definitions

To achieve the first objective, we will perform hypothesis tests for comparisons of each intervention to placebo, (independently of the other interventions) for each of the two primary endpoints (defined below). An intervention will be considered efficacious if significant benefit is found with respect to either of the two primary endpoints. To achieve the second objective, we will enroll participants inside

and outside the target subgroups and optimize the target subgroup definitions using precision medicine methods.

The study also has two secondary objectives:

1. Gain information about potential monitoring biomarkers for selected therapies
2. Explore the safety and effectiveness of selected therapies in adolescent patients with severe asthma

For the first secondary objective, we will identify which monitoring biomarkers could potentially serve as early or intermediate outcomes for an investigation. These biomarkers may prove useful in predicting whether a drug will be effective with respect to clinical outcomes, which could in turn inform future trials of the drug. For the second, we will describe trends with respect to the primary efficacy outcomes observed in the adolescent subgroup and determine if the risk profile of an intervention appears to differ between adults and adolescents. We do not expect to have sufficient power for formal hypothesis tests of effects in the adolescent subgroup alone or for a test of age by treatment interactions.

For both primary objectives, we have defined two primary endpoints:

- 1) FEV₁ percent predicted, assessed prior to bronchodilator administration (primary)
- 2) Asthma symptom control, assessed via the Juniper Asthma Control Questionnaire (ACQ-6) (primary)

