3.5 Study Definitions and Created Variables

3.5.1 Visits

- Baseline visit is Visit X.1, where X indicates the treatment period and ranges from 1 to 6.
- Endpoint visit is Visit X.5, where X indicates the treatment period and ranges from 1 to 6.
- On-treatment visits are monthly and include Visits X.2, X.3, X.4, and X.5
- Visit windows for baseline and on-treatment visits are ± 5 days

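### SAP 7.9.2 reuses the overall safety tables for adolescents, whose required on-treatment labs and brief exams are half as frequent as adults', so laboratory and exam abnormality incidences are not comparable by age.

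*SAP*

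**What the plan says.** - **Visits.** SAP 3.5.1: "On-treatment visits are monthly and include Visits X.2, X.3, X.4, and X.5".
- **Schedule by age.** In Protocol 1.3, the row "Blood: CBC with Differential Count", the chemistry and liver-test row and the brief physical exam row all carry footnote 4 at X.2 and X.4. The footnote reads: "Not required for adolescents at VX.2 and VX.4". The amendment history (Protocol 10.4) dates this change to version 3.0 (November 2021) for the labs and version 3.1 (February 2023) for the exam.
- **Adults.** Protocol 7.1.1: "For adults, the below lab tests will be assessed at every 4-week visit during the treatment period".
- **Adverse events.** Protocol 8.3.5.4 applies to all ages: "At each study visit, the investigator will inquire about the occurrence of AE/SAEs since the last visit". The adverse event row of the schedule has no adolescent footnote.
- **Objective.** SAP Section 2, like Protocol Section 3, intends to "determine if the risk profile of an intervention appears to differ between adults and adolescents".
- **Analysis.** SAP 7.9.2: "Safety data will also be described and analyzed separately for the adolescent population using the same tables and graphics described for the overall population". SAP 7.6 summarises safety endpoints, laboratory parameters included, as differences from placebo with 95% confidence intervals. Neither section mentions the different schedules, a set of common visits, or a denominator of tests performed.

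**The concern.** The chance that a participant has at least one abnormal result in a 16-week period rises with the number of times the participant is tested. If adults are tested four times on treatment and adolescents twice, identical tables give different incidences at identical true risk. The lower figure always falls on the adolescents.

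The same applies to the absolute difference between active and placebo when a drug really does cause transient abnormalities, and that difference is the summary the SAP names. Adverse events found only through a lab, and removals from treatment that begin with a scheduled lab, can be affected too.

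The contrast at stake is the adult-adolescent safety judgement for MCT and Broncho-Vaxom, the two interventions studied in both age groups. A reader who sets the two sets of tables side by side could take a difference in testing for a difference in risk.

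**Working it through.** The plan gives no figure for this point, so there is nothing to reproduce. The check counts tests and then asks what the count does to incidence.

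**1. Required on-treatment tests per period** (Protocol 1.3 with footnote 4; SAP 3.5.1)
- Adults: X.2, X.3, X.4, X.5, so k = 4.
- Adolescents: X.3, X.5, so k = 2.
- Ratio: 2/4 = 0.50. Counting the washout visit X.6 as well it is 3/5 = 0.60, and over X.1 to X.6 it is 4/6 = 0.67.

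**2. Transient abnormality, equal true risk.** Assumption: probability p per test, independent across visits. The documents give no value for p, so a range is shown. Incidence of any abnormality = 1 − (1 − p)^k.

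| p per test | Adults, k = 4 | Adolescents, k = 2 | Ratio |
|---|---|---|---|
| 1% | 3.9% | 2.0% | 0.51 |
| 2% | 7.8% | 4.0% | 0.51 |
| 5% | 18.5% | 9.8% | 0.53 |
| 10% | 34.4% | 19.0% | 0.55 |
| 20% | 59.0% | 36.0% | 0.61 |

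For p = 5%: 1 − 0.95^4 = 0.1855 and 1 − 0.95^2 = 0.0975.

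**3. Abnormality that persists.** Assumption: one episode of D weeks, with onset uniform over 16 weeks, sampled at weeks 4, 8, 12, 16 (adults) or 8, 16 (adolescents). Detection probability is min(1, D/4) in adults and min(1, D/8) in adolescents.
- D up to 4 weeks: ratio 0.50.
- D = 6 weeks: 1.00 against 0.75, ratio 0.75.
- D of 8 weeks or more: ratio 1.00.

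**4. Active against placebo within an age group** (same assumption as step 2)

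| Per-test risk, active / placebo | Adult difference | Adolescent difference |
|---|---|---|
| 5% / 5% | 0 | 0 |
| 5% / 2% | 18.55 − 7.76 = 10.8 points | 9.75 − 3.96 = 5.8 points |
| 8% / 3% | 28.4 − 11.5 = 16.9 points | 15.36 − 5.91 = 9.5 points |

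A null effect stays null. With a real effect, the absolute difference is roughly halved. The risk ratio is about preserved: for 5% against 2% it is 2.39 in adults and 2.46 in adolescents.

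**5. After restriction to X.3 and X.5.** With k = 2 in both groups, p = 5% gives 9.8% in adults and 9.8% in adolescents. Per assessment performed, it gives 5% in both.

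**The case against.** A reader might infer that adolescents will look safer by construction across the whole risk profile. The documents do not support that.
- Adverse events and SAEs are asked about at every visit for all ages, so symptomatic events, exacerbations and hospitalisations are collected on one schedule.
- Changes from X.1 to X.3 or X.5, by-visit summaries and abnormalities lasting 8 weeks or more are unaffected.
- Within an age group, active and placebo periods share a schedule, so a drug with no effect does not acquire one.

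Other replies also carry weight.
- SAP 7.6 does not say that laboratory results will be tabulated as any abnormality in the period. The artefact arises only in tables of that kind.
- Most lab criteria for removal in Protocol 7.1.1 need two sequential abnormal values, so the ratio of about 0.5 cannot be carried over to discontinuations.
- Tests that are not required may still be drawn, the COVID-19 note to the schedule means adults may not always have four, and intervention-specific labs sit in appendices not available here.

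The last reply is that about 40 adolescents are expected and the analysis is descriptive. Even with all 40 on one drug, a 9.75% incidence has a 95% half-width of 1.96 × √(0.0975 × 0.9025 / 40) = 9.2 points, against an artefact of 18.55 − 9.75 = 8.8 points. That limits how much any reader should conclude, but it does not remove the problem. Sampling error has no fixed direction, whereas this shift does. The age judgement is a stated objective, and it will be made by eye from these tables.

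**Conclusion.** The point holds for laboratory and brief-exam abnormalities only. Required on-treatment assessments number two in adolescents and four in adults, the same tables serve both groups, and the SAP is silent on the difference. Where results are shown as any abnormality in the period, the adolescent-to-adult ratio at equal true risk is about 0.5 for transient abnormalities (0.51 to 0.61 for an assumed 1% to 20% per test) and rises to 1.0 once abnormalities last 8 weeks or more. Absolute differences from placebo shrink in a similar way if there is a real transient effect.

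These sizes rest on assumed rates, durations and independence between visits, and on the required schedule being the one followed. Lab-detected adverse events and lab-triggered removals may also be lower in adolescents, by an amount the documents do not allow one to state.

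This is worth correcting because the remedy is cheap and the comparison is a declared objective. It does not bear on the primary efficacy analysis.

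**What to change.** Add to SAP 7.9.2:
- Adult-adolescent comparisons of laboratory and exam abnormalities are displayed on X.3 and X.5 in both groups. X.2 and X.4 values are left out of this display, including any that adolescents have from before the schedule change.
- Adults who left treatment for an X.2 or X.4 abnormality count as having an event. Without this rule, restricting to X.3 and X.5 would drop the adults with early toxicity and understate adult risk.
- The same abnormalities are also shown per assessment performed, with scheduled assessments as the denominator, because Protocol 7.1.1 triggers extra retests after an abnormal value.
- A note states that lab-triggered adverse events and discontinuations were ascertained on different schedules in the two age groups. The adverse event items listed in Protocol 8.3.5.4 include no marker of detection by lab, so these cannot simply be filtered by visit.
- The full-schedule table remains the main adult safety table.

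The cost is a few sentences and one extra descriptive table, with adult X.2 and X.4 values unused in the common-visit display apart from the removals counted above. Counting those removals leaves a small asymmetry, since an adolescent abnormality that resolved before X.3 would still be missed; the per-assessment display helps to show how much that matters. No new data are needed and the monitoring schedule does not change.

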7.9.3 Subgroup Analysis Using Proximal Biomarkers

We will repeat the precision medicine analysis described in Section 7.7.3 using primary predictive biomarkers assessed right before the start of each intervention. Using the power for the treatment comparison in the best subgroup, we will compare the predictive ability of baseline biomarkers versus more proximal biomarkers. If additional potentially predictive biomarkers emerge by the time of this final analysis, the analysis will be repeated after addition of these biomarkers to the set of primary and secondary predictive biomarkers.

7.9.4 Precision Medicine Analyses for Interventions with Overlapping Target Subgroups

Once all interventions not stopped early for futility have been completed and data are available, an exploratory precision medicine analysis to estimate individualized treatment rules will be performed for severe asthmatics with different biomarker profiles. As noted above, the primary efficacy analyses for the PrecISE study involve comparisons of each intervention to placebo, conducted independently of the other interventions, with no comparisons of one intervention to another. In an exploratory fashion,

however, interventions that were found to be significantly better than placebo and whose estimated best target subgroups overlap will be analyzed to identify the best intervention in each overlapping region. For example, suppose the target subgroups for two interventions both include patients with high IL-6 plasma levels and high blood eosinophils. In that case, exploratory analyses will be conducted to determine if either appears to provide superior benefit in that overlapping subgroup region.

Results of the study's primary analyses will include estimated decision rules for each participant identifying which interventions' target subgroups the participant belongs to. That is, a set of functions mapping the patients' biomarkers to a set of indicators on whether or not each intervention is better than placebo will be determined for each participant in the study. All biomarkers involved in defining the target subgroups will be combined with standard demographic variables to define a vector of patient tailoring variables \mathbf{X} to ensure comparability and compatibility across successful treatments. If there are any intersections of these subgroups which are non-empty for two or more treatments, an exploratory precision medicine analysis will further refine the subgroups to assign patients to the one treatment (or multiple essentially equivalent treatments) that dominates all other treatments. Potential methods for this exploratory analysis include random forests,¹² linear regression models with quadratic terms and interactions, and outcome weighted learning models.^{13,14} Equivalence of two treatments for a given value of \mathbf{X} will be defined as a difference in expected outcome Y for those two treatments of less than 10% of the overall standard deviation of outcome.

Formally, two treatments A_j and $A_{j'}$, are defined for $j \neq j'$ to be equivalent if $|E[Y|\mathbf{X} = \mathbf{x}, A = a_j] - E[Y|\mathbf{X} = \mathbf{x}, A = a_{j'}]| < 0.1\hat{\sigma}_Y$, where $\hat{\sigma}_Y$ is the overall standard deviation of the outcome Y . This analysis will be done separately for each of the three outcomes. Results from this analysis will allow future treating clinicians to determine which intervention or interventions are best for each of the three outcomes for a patient with feature value $\mathbf{X} = \mathbf{x}$.

One challenge with the above approach is that a treating clinician will need to prioritize among the three outcomes (FEV₁ asthma symptoms, and loss of asthma control), for a given patient. To address this, precision medicine analysis will also be conducted combining the three outcomes. Let \mathbf{Y} be the vector of the three outcomes, rescaled so that larger values correspond to better outcomes. Specifically, for a given outcome, if larger values indicate a better outcome, the outcome remains as is; otherwise, if larger is worse, then the negative of the outcome will be used. Let \mathbf{W} be a vector of three weights between 0 and 1 whose total adds up to 1. For each possible value of \mathbf{W} (over a fine grid), the outcome weighted analysis described in the previous paragraph is repeated, including placebo as a treatment. All treatments are simultaneously compared by dividing the feature space, \mathbf{X} , into regions wherein each of the treatments is optimal for the outcome $\mathbf{W}'\mathbf{Y}$, the inner product of \mathbf{W} and \mathbf{Y} , with null regions allowed. The expected value of the resulting treatment rule is then estimated for each of the three outcomes separately using the value estimation procedure¹³, and this is repeated over all distinct values of \mathbf{W} on the grid, where m denotes the number of distinct values. A table is then created with three columns, one for each outcome, and m rows, one for each distinct value on the grid, where each entry in the table corresponds to the estimated value function for the given outcome and grid value. For each of the three columns, value function estimates are replaced by their percentiles across the m rows within each column. Now for each row, the minimum percentile across the three columns is determined, and the value of \mathbf{W} corresponding to the row that maximizes this minimum is called \mathbf{W}_* . This is the best performing combination overall in the sense that every other value of \mathbf{W} will yield a lower percentile for the worst performing outcome. This is the "minimax" optimal choice of \mathbf{W} , and all of the analyses of the previous paragraph are repeated, including the equivalence determinations, for the weighted outcome $\mathbf{Y}_* = \mathbf{W}_*'\mathbf{Y}$. This will provide an alternative clinical decision which combines the three outcomes.

References

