The best subgroup for an intervention is defined as the subgroup that maximizes the power of detecting a treatment effect under the global null hypothesis relative to its alternative, namely, the null hypothesis that the intervention has no effect on the two primary endpoints, FEV₁ and ACQ-6, and the key secondary endpoint, CompEx, versus the alternative hypothesis that there is an effect on at least one of these endpoints. For a single outcome, this definition is equivalent to maximizing the square root of the size of the subgroup measured by its prevalence in the relevant patient population multiplied by the average treatment effect in the subgroup. This approach to defining the best subgroup reflects not only the treatment effect in the subgroup but also the size of the subgroup. Potential target subgroups with prevalence smaller than 16% will not be considered.

The primary predictive biomarkers are: blood eosinophils for imatinib, interleukin 6 for clazakizumab, genotypes rs7669660 and rs11547772 for cavosonstat, blood eosinophils for Broncho-Vaxom, and fractional exhaled nitric oxide (FeNO) for MCT. For each of the three outcomes, FEV₁ and ACQ-6 and CompEx, a model like the primary analysis model is fit that includes fixed effects for each biomarker, two-way interactions among the biomarkers, the biomarkers' interactions with treatment, and the biomarkers' two-way interactions with treatment. The one (1) standard deviation method¹⁰ and the overlapping group exponential Lasso penalty approach¹¹ with a penalty term that leads to more likely selection of subgroups defined by a smaller number of biomarkers will be used. Three models will be fitted, one for each outcome. From the fitted model for outcome Y_j , $j = 1, 2, 3$, a set of estimated linear predictors, $\hat{\eta}_1, \dots, \hat{\eta}_n$, is obtained for the set of biomarker vectors through plugging in estimated model coefficients. The target subgroup is then estimated based on a weighted average of three test statistics,

one for each outcome. The best subgroup is the subgroup that maximizes the power of the hypothesis test.

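### SAP 7.9.4 reads membership of the power-maximising subgroup as benefit over placebo, so patients with a smaller but real benefit can be labelled as having none

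*SAP*

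**What the plan says.** SAP 7.8 sets the criterion: "The best subgroup for an intervention is defined as the subgroup that maximizes the power of detecting a treatment effect". For a single outcome this amounts to maximising "the square root of the size of the subgroup measured by its prevalence in the relevant patient population multiplied by the average treatment effect" among its members, and the section says openly that size counts as well as effect. With several outcomes, "The target subgroup is then estimated based on a weighted average of three test statistics". There is also a floor: "Potential target subgroups with prevalence smaller than 16% will not be considered". The result is to be reported as the type of patient to target, and as a guide to the design of later studies.

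SAP 7.9.4 uses these subgroups to build treatment rules. The decision rules are described as "identifying which interventions' target subgroups the participant belongs to". The next sentence restates them as "a set of indicators on whether or not each intervention is better than placebo". The comparison between drugs is then conditional on overlap: "If there are any intersections of these subgroups which are non-empty for two or more treatments", the regions are refined to find the treatment that is best there. Two treatments count as equivalent at a given X if their expected outcomes differ by less than 0.1 SD.

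The last part of 7.9.4 combines the three outcomes with weights. It compares all treatments, with placebo included, over the whole feature space. It does not say whether the restriction to overlapping subgroups still applies.

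SAP 7.7.3 and Protocol 9.5.6 expect the effect outside the target subgroup to be smaller. Neither says it is absent.

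**The concern.** A subgroup that maximises power is a sensible enrichment target, but it is not the set of patients who benefit. Adding patients with a modest benefit enlarges the subgroup and lowers its average effect. Below a certain point the second change outweighs the first, and the criterion drops those patients although the drug helps them. When 7.9.4 reads non-membership as not better than placebo, it gives these patients a label that the criterion does not justify.

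The reported treatment rules are what is at stake. SAP 7.9.4 intends them to help clinicians decide which intervention suits which patient. In the single-outcome overlap step, a drug whose subgroup omits a patient is not in the comparison for that patient, even if its benefit there exceeds that of the drug that remains.

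**Working it through.** **Inputs.** The criterion comes from SAP 7.8. The prevalences come from SAP Table 1: clazakizumab 33%, Broncho-Vaxom 38%, imatinib 62%, cavosonstat 64%, MCT 64%. The design effect of 0.3 SD comes from SAP section 5, and the 0.1 SD margin from SAP 7.9.4. The plan gives no effect curve over the biomarkers, so every curve below is an assumption. All results are error-free limits, before sampling noise.

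**The plan's own figure.** 4.3/14.5 = 0.297 for FEV1 and 0.18/0.6 = 0.300 for ACQ-6, which agrees with the stated 0.3 SD.

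**Continuous ranking, one outcome.** Rank patients from largest to smallest effect. Let S(p) be the cumulative effect in the top fraction p. The average is S(p)/p, so the criterion is C(p) = √p × S(p)/p = S(p)/√p. Setting dC/dp = 0 gives effect at the edge = S(p)/(2p), which is half the subgroup average. The same holds for a fixed weighted sum of standardised outcomes.

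The share of all patients left out despite a positive effect depends on the curve:

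| Assumed effect curve | Share left out with positive effect |
|---|---|
| Linear, falling to 0 | 33% |
| Exponential | 63% |
| Normal, mean 1, SD 1 | 28% |
| Linear, 1.7 to 0.3 | 19% |
| Linear, 1.5 to 0.5 | 0% |

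In the last row nobody lies below half the average. The 16% floor does not bind in any row.

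Worked case, linear to 0: with effect proportional to 1 − u, the average over the top p is proportional to 1 − p/2. The edge condition 1 − p = (1 − p/2)/2 gives p = 2/3. If the subgroup average is 0.3 SD, the edge is 0.15 SD and the excluded third have effects from 0 to 0.15 SD. Those above the 0.1 SD margin are (1/3) × (0.05/0.15) = 11% of all patients.

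**Two groups.** Let positives have prevalence p and effect d, and negatives effect r × d. Positives alone score √p × d. Everyone together scores [p + (1 − p)r] × d. Negatives are left out if r < (√p − p)/(1 − p) = √p/(1 + √p). With d = 0.3 SD:

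| Intervention | p | Limit on r | In SD | FEV1 points (× 14.5) | ACQ-6 units (× 0.6) |
|---|---|---|---|---|---|
| Clazakizumab | 0.33 | 0.365 | 0.109 | 1.59 | 0.066 |
| Broncho-Vaxom | 0.38 | 0.381 | 0.114 | 1.66 | 0.069 |
| Imatinib | 0.62 | 0.441 | 0.132 | 1.92 | 0.079 |
| Cavosonstat, MCT | 0.64 | 0.444 | 0.133 | 1.93 | 0.080 |

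**Coarse cutoffs.** When a block extends the subgroup from prevalence p1 to p2, the limit is √p1/(√p1 + √p2). For five equally spaced quantile cutoffs this runs from 0.41 to 0.48.

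**Effect on a comparison (assumed values).** Drug A averages 0.6 SD in its subgroup, so its edge is 0.30 SD. Drug B averages 0.25 SD, so its edge is 0.125 SD. A patient with true effects of 0.28 SD on A and 0.13 SD on B belongs only to B's subgroup. The rule says that A is not better than placebo and does not compare it, although A is better by 0.28 − 0.13 = 0.15 SD, more than the 0.1 SD margin.

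**The case against.** The best defence has four parts.

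- **The combined-outcome step.** A reader might infer that an excluded drug is never compared with another in the excluded patients. The documents do not support that. The last part of 7.9.4 compares all treatments and placebo over the feature space and states no overlap restriction, so the drug may re-enter there. The loss of comparison is explicit only in the single-outcome overlap step, and the later step does not correct the indicator.
- **Effects outside the subgroup are estimated elsewhere.** SAP 7.4.1 estimates subgroup-specific effects through an interaction, and 7.7.1 tests biomarker negatives alone at the interim. This is true, but 7.9.4 does not feed either result into its indicator.
- **The size is uncertain.** This stands. One half is exact only for a continuous ranking; coarse cutoffs and two-group splits give lower ratios. Using the 67% enrolment share would give 0.45, but the SAP 7.8 criterion uses prevalence in the patient population, and no intervention in Table 1 exceeds 64%.
- **The section is exploratory.** It compares only interventions already found significantly better than placebo whose subgroups overlap. This also stands and limits the weight of the point.

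A reader might also think it enough to call a drug better than placebo wherever the 7.8 model gives an effect above 0. That would not do. The 7.8 model is Lasso-penalised, is described without the demographic variables that belong to X, and offers no error control at a single X. Where the true effect is zero, about half of unbiased estimates would exceed 0.

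**Conclusion.** The point holds as an error of interpretation in SAP 7.9.4. The power criterion is reasonable for enrichment; reading non-membership as no benefit over placebo is not. The boundary lies at half the subgroup average on a continuous ranking, at 0.41 to 0.48 for five equally spaced quantile cutoffs, and at 0.36 to 0.44 for two-group splits at the Table 1 prevalences. The last range means about 0.11 to 0.13 SD if positives gain 0.3 SD, which is slightly above the section's own 0.1 SD margin.

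How many patients are mislabelled rests on an effect curve that the plan does not give. The assumed curves range from none to 63%. Sampling noise would add errors in both directions.

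Nobody should infer that the trial's efficacy conclusions are at risk. The primary tests, their Type I error and the sample size do not use this indicator. What can change is the content of the exploratory treatment rules.

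**What to change.** In SAP 7.9.4:

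1. Call the indicator membership of the estimated target subgroup, and state that non-membership is not evidence of no benefit over placebo.
2. Run the single-outcome comparisons in the same way as the combined-outcome step: all interventions found effective, plus placebo, over the full feature space X, with the methods the section already names.
3. Base any statement that a drug is better than placebo at X on that estimated contrast. Report it with its uncertainty and label it exploratory.
4. State that the combined-outcome step is not restricted to intersections of subgroups.

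Keep the best subgroup of SAP 7.8 unchanged as the enrichment target for later studies.

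The cost is SAP wording and some extra exploratory analysis, with no new data. Estimates outside the subgroups will be noisier. This applies most where few biomarker negatives were treated, as for cavosonstat, which SAP 7.4.1 names as the case in which the negative subgroup is dropped after the interim.
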